#### 5.4 Safety Assessment

Both IIV and Tdap administration for pregnant women are recommendations for routine clinical care during pregnancy such that we do not anticipate having a significant issue with SAEs. However, we will monitor study participants for medically-attended events and SAEs during the protocol-defined surveillance period of vaccination through delivery. Subjects will be followed for SAEs up to the 6-week postpartum visit. Significant infant complications or SAEs identified during the delivery visit will be followed up to the 2 month Well Child Visit.

An SAE is defined as an AE that meets one of the following conditions:

- Results in death (maternal, fetal, or infant) during the study period

- Is life-threatening (defined as immediate risk of death at the time of the event)
- Requires inpatient hospitalization prolongation of hospitalization during the study period (other than routine hospital admission for labor & delivery)
- Results in congenital anomaly or birth defect
- Results in a persistent or significant disability/incapacity
- Any other important medical event that may not result in death, be life threatening, or require hospitalization, may be considered an SAE when, based upon appropriate medical judgment, the event may jeopardize the subject and may require medical or surgical intervention to prevent one of the outcomes listed above. Examples of such medical events include allergic bronchospasm requiring intensive treatment in an emergency room or at home, blood dyscrasias or convulsions that do not result in inpatient hospitalization, or the development of drug dependency or drug abuse.

SAEs will be reported to the CDC, Duke, and Cincinnati Children's IRBs within 48 hours of study staff awareness of the event. If indicated, SAEs will be reported to the CDC's Vaccine Adverse Event Reporting system (VAERS).

Given that this is a pilot study involving vaccines that are included as part of routine clinical care, there will not be a designated data safety monitoring board for this pilot study. If deemed necessary, we will designate an independent safety monitor with relevant expertise, in collaboration with the CDC.

## **5.5 Biospecimens Collection & Handling**

### **5.5.1 Serum**

Maternal and cord blood specimens will be collected during study visits as described in **Table 1**. All blood samples will be collected, processed, and frozen according to the standard operating procedures and not contain personal identifiers. Serum aliquots will be frozen and stored at each site until planned laboratory analyses. A portion of serum aliquots from each subject's blood draw visits will be sent to the CDC for Pertussis assays once all study samples have been collected for all subjects. Remaining frozen serum aliquots will be stored and then shipped to the lead site for influenza, tetanus, and diphtheria assays. Please refer to the study's manual of operations for specifics of sample shipping to CDC and Duke University.

The Study site(s) will process and ship these samples to CDC using standard procedures, in accordance with specimen transport policies (<http://www.cdc.gov/laboratory/specimen-submission/shipping-packing.html>). The study site(s) will use the CDC File Accessioning Form to send the specimen data via e-mail to [name] ([[contact]](mailto:[contact])) or designee. All samples will be barcode labelled and contain a unique ID and date and time of sample collection. No personal identifiers will be included on the samples or CDC File Accessioning Form.

Any unused serum samples will be returned to the study site(s) after all assays have been completed.

### 5.5.2 Placental Tissue

The study team will work with labor and delivery staff to ensure placentas from study subjects are sent for pathological evaluation for chorioamnionitis. The results from the pathology reports will be entered into REDCap.

Following delivery of all subjects, placental histological slides will be over-read for histological diagnosis of chorioamnionitis. Over-reading will be performed by a single board-certified pathologist with expertise in placental pathology at Duke University. The pathologist will be blinded to study details including randomization arm assignment. Chorioamnionitis will be assessed using the grading scale described in **Table 5**. If a clinically-significant discrepancy is noted between the original pathology report regarding chorioamnionitis and the over-read by the blinded pathologist, then another independent pathologist will review the pathology slides in question to allow for adjudication of the discrepant results.

### 5.5.3 Infant Dried Blood Spots

The study team will obtain a blood sample via heel stick on a subset of 10 infants at each site (20 total) to collect 5 dried blood spots to determine levels of IgG to pertussis toxin, filamentous hemagglutinin, and pertactin (the pertussis antigens in the Boostrix® vaccine) at the CDC. DBS punch cards will be adequately dried with desiccant provided by the CDC and shipped to the CDC for pertussis testing. CDC pertussis laboratory will destroy unused DBS after all assays and the study have been completed.

## 6 LABORATORY ANALYSES

### 6.1 Pertussis Laboratory Analysis

Quantification of antibodies against pertussis toxin (PTx), pertactin (PRN), filamentous hemagglutinin (FHA), and fimbrial antigen 2/3 (Fim2/3) in a microsphere based multiplex antibody capture assay according to CDC protocol MPIR-4301. Antibody to fimbrial antigen 2/3 will only be done on samples collected in 2016-2017 influenza season. All specimens will be run in duplicate by 2 independent operators. Briefly, each of the 5 antigens are conjugated to spectrally distinct fluorescent microspheres (Luminex XMAP™, Austin, TX). The microspheres are incubated with serum for 40 minutes at room temperature, washed, then incubated for 20 minutes with a fluorescently labelled anti-human antibody. The beads are then washed again and read using a Luminex instrument. Antibody levels are quantified by interpolation to a WHO reference standard. Samples that read higher than the useable range of the reference standard are repeated at a higher starting dilution. The independent results are compared, and if the coefficient of variation (CV) is below 30% the mean is reported. If the CV is greater than 30%, up to 2 additional runs are performed and the median is reported.

### 6.2 Tetanus and Diphtheria Laboratory Analysis

Quantification of antibodies against diphtheria and tetanus toxoids will be performed by ELISA using kits containing an internal standard (AbCam, Cambridge, MA) per the manufacturer's directions. Briefly, wells pre-coated with diphtheria or tetanus antigen are incubated with dilution media as a blank, control specimens that contain a defined amount of anti-diphtheria or anti-tetanus antibody, or an unknown test sample. All specimens are run in duplicate. Primary antibody is allowed to bind for 1 hour at 37°C, plates washed, and secondary antibody allowed to bind for 30 min at room temperature.

Plates are washed again and substrate added; this is incubated for 15 min at room temperature in the dark, followed by reading on a microtiter plate reader at 450 nm. The values from replicate wells are averaged, the background of blank wells subtracted from all other wells, and a dilution curve created using the known controls. Optical density readings are then compared to the standard curve and an absolute value for binding antibodies in international units is calculated. For specimens that have optical density readings higher than the standard curve range, a dilution of the serum/plasma sample is assessed in a repeat assay.

### **6.3 Influenza Laboratory Analysis**

We intend to utilize the 2016-2017 and 2017-2018 quadrivalent Fluzone (Sanofi) as the IIV study product. As such, reference wild-type, reassortant, or vaccine virus strains representative of the specific viral antigens included in the 2016-2017 and 2017-2018 influenza vaccines will be used to evaluate the relative levels of all four influenza strain-specific antibodies in maternal serum pre- and post-vaccination (60 subjects, 240 samples total). To accomplish these activities all patient samples will be interrogated for influenza antibodies against the strains of interest using the influenza hemagglutination inhibition assay (HI). This assay is considered the “gold-standard” measure by which to evaluate seroconversion/seroprotection in response to seasonal influenza vaccination. This assay will be performed in accordance with the RBL Virology Unit’s fully optimized and approved SOP (RVUSOP004 Influenza HI of Serum Samples). Briefly, test samples will be assayed by HAI as duplicate 2-fold dilution series starting at 1:10. Serum dilutions are then incubated with a concentration of virus verified to possess a known potential for red blood cell (RBC) agglutination. The presence of virus-specific antibodies is visualized via incubation of the virus-serum mixture with a RBC solution; the endpoint titer for a given dilution series is then expressed as the reciprocal of the final dilution in which complete HI is observed. By convention, seronegative samples are defined as having an endpoint HI titer < 1:40 and seropositive samples as having an endpoint titer of ≥ 1:40; and seroconversion as a 4-fold change in endpoint titer relative to pre-immunization baseline or a change from <1:10 to ≥1:40.

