**PROTOCOL SUMMARY**

Title:	A Prospective, Randomized, Open-label Clinical Trial to Assess the Safety and Immunogenicity of Simultaneous versus Sequential Administration of tetanus toxoid, reduced diphtheria toxoid, and acellular pertussis vaccine and inactivated influenza vaccine in Pregnant Women – Pilot
Phase:	Phase 4
Population:	80 adult pregnant women (18-45 years) at $\geq$ 26 weeks 0 days gestation through $\leq$ 32 weeks 0 days gestation who plan on receiving Tdap and IIV during the current pregnancy in accordance with the Advisory Committee on Immunization Practices (ACIP) and American College of Obstetricians & Gynecologists (ACOG) national recommendations.
Clinical Sites:	Two: Duke University (Lead); Cincinnati Children's Hospital Medical Center (Contributor)
Study Duration:	24 months (4 months to recruit/enroll (per flu season), maximum of 26 weeks to follow (5.5 months) (per flu season), 4.5 months to perform analysis and laboratory assays (per flu season))
Participant Duration:	Up to 23 weeks depending upon gestational age at enrollment and delivery
Description of Study Procedures:	
This is a pilot, prospective, randomized, open-label clinical trial. During the study, pregnant women will be randomized (1:1) to receive co-administration of a single intramuscular (IM) 0.5 mL dose of US-licensed inactivated influenza vaccine (IIV) and a single intramuscular (IM) 0.5 mL dose of US-licensed Tetanus toxoid, reduced diphtheria toxoid and acellular pertussis vaccine adsorbed (Tdap) or sequential administration of the vaccines (IIV followed by Tdap ~ 21 days later). Vaccines will be administered by licensed study personnel.
 
Prior Tdap/Td/TT and influenza vaccine history will be verified by medical record review when possible.
 
Injection-site (local) and systemic reaction data will be assessed on vaccination day and during the 7 days following vaccination using either identical web-based or paper diaries, depending on study participant preference.
 
Maternal serum samples will be collected for antibody titers relevant to the Tdap and Influenza at time points that include: prior to vaccination(s), ~22 days post vaccination(s), and at

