### 2.1 Study Outcome Measures

#### 2.1.1 Primary Outcome Measures:

- Proportions of injection-site and systemic reactions will be compared in simultaneous and sequential groups
- Measurement of serum antibody levels to pertussis antigens (pertussis toxin, filamentous hemagglutinin, and pertactin), diphtheria and tetanus toxoids, and influenza antigens in:
  - Maternal blood pre and post-vaccination in pregnant women
  - Maternal and infant cord blood obtained at delivery
- Feasibility benchmarks to assess participant recruitment/retention and adequate, timely collection of data and biospecimens

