## 3 STUDY DESIGN

### 3.1 Main study design

This pilot study is a prospective, randomized open-label clinical trial of approximately 80 healthy pregnant women enrolled at Duke University Medical Center (Lead Contractor) and Cincinnati Children's Hospital (Contributing Contractor) who will be followed after they receive simultaneous or sequential single 0.5 mL intramuscular (IM) dose of US-licensed inactivated influenza vaccine (quadrivalent Fluzone) and single 0.5 mL intramuscular (IM) dose of US-licensed tetanus toxoid, reduced diphtheria toxoid and acellular pertussis vaccine (Tdap, Boostrix). In each study participant, the Tdap and IIV vaccine that is administered will be produced by different manufacturers unless there are manufacturing issues or vaccine shortages that necessitate acquisition of Tdap and IIV from the same manufacturer.

Pregnant women 18-45 years of age and 26-32 weeks gestation will be enrolled over a period of approximately 4 months per flu season. The purpose of the study is to compare the rates of injection-site and systemic reactions and the immune response following simultaneous administration of IIV and Tdap or sequential administration of IIV followed by Tdap in pregnant women, and to assess rates of adverse pregnancy (maternal and infant) outcomes including, but not limited to, preterm birth, small for gestational age (SGA), and chorioamnionitis. Maternal and infant outcomes will be collected by medical record review from enrollment through hospital discharge following delivery.

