**Visit 1, Study Day 1 (Vaccination Day) - Screening, Enrollment, and Randomization (Clinic Visit)**

- If Screening Visit occurred prior to Visit 1, review and confirm eligibility and all data collected during Screening Visit
- Obtain vital signs including oral temperature prior to vaccination
- Obtain 15mL blood sample prior to vaccination for serologic analysis (Section 6)
- Randomize study participant to simultaneous or sequential vaccine administration (Section 5.2.1)
- Administer assigned study products – Trained, licensed research staff will administer either IIV alone or IIV + Tdap as described in Section 5.2.3. Ensure participants receive corresponding Vaccine Information Sheets (VIS) during visit.
- Dispense memory aid (Appendix B and C), thermometer, and ruler (in order to standardize measurements). Review instructions for use of thermometer, ruler, and

memory aid (Appendix A) completion.

- Confirm preferred method of contact for follow-up (telephone, text or email reminder)
- Confirm date of next scheduled prenatal appointment
- Record any AEs and SAEs during post-vaccination monitoring

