**Visit 4, Study Day 22 (window Days 22 – 29) Clinic Visit**

- For study participants in the sequential study group, review exclusion criteria listed in section 4.2 for Tdap vaccination
- Obtain vital signs including oral temperature prior to vaccination for study participants in the sequential group.
- Study staff will review the memory aid data and record any AEs, SAEs, concomitant medications, and current medical/pregnancy status as described in Section 5.1
- Obtain 15mL blood sample for serologic analysis (Section 6). Study participants in sequential group to have blood sample obtained prior to vaccination.
- For subjects in the sequential study group, trained, licensed research staff will administer Tdap as described in Section 5.2.3. Ensure participants receive Tdap Vaccine Information Sheets (VIS) during visit.
- Confirm subjects still have previously dispensed thermometer and ruler; if not, provide new supplies. Review instructions for use of thermometer, ruler, and memory aid (Appendix A) completion. All subjects will complete the memory aid (Appendix D and E) again to allow for the collection of “mock” data in the simultaneous group for comparison with the sequential group. Simultaneous group will only provide information for systemic reactions and oral temperature.

- Confirm preferred method of contact for follow-up (telephone or email reminder)
- Confirm date of next scheduled prenatal appointment

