**Visit 6, Study Day 30 - 37 (window Days 30 – 40) Phone Call/Email/SMS Text Follow-Up**

Study staff will contact study participants (Appendix F) to review the memory aid data and record any AEs, SAEs, concomitant medications, and current medical/pregnancy status as described in Section 5.1. Participants who are lost to follow-up by phone contact will continue to be called on a weekly basis until approximately Day 45 following vaccination for safety assessment. Study staff will also approach participants at follow-up prenatal appointments which should be within 2-4 weeks based on routine prenatal care guidelines.

**Visit 7, Study Day 43 - 50 (window Days 43 – 57) Clinic Visit for sequential group, Phone Call/Email/Text for simultaneous group**

- This review will be done by phone call/email/text for study participants (Appendix F) in the simultaneous group and in clinic for participants in the sequential group. Study staff will review the memory aid data and record any AEs, SAEs, concomitant medications, and current medical/pregnancy status as described in Section 5.1. Obtain 15mL blood sample for serologic analysis for sequential group only (Section 6)

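### Does the count of 60 subjects and 240 samples in Section 6.3 leave the scope of the influenza antibody testing in doubt?

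*Combined protocol and SAP*

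**What the plan says.** Section 6.3 says that strain-specific antibody against all four vaccine strains, for both influenza seasons, will be measured in maternal serum before and after vaccination, and adds in parentheses "60 subjects, 240 samples total". The next sentence states that "all patient samples will be interrogated for influenza antibodies against the strains of interest".

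Planned enrollment is larger. The Protocol Summary gives "80 adult pregnant women (18-45 years" and Section 3.1 describes a "randomized open-label clinical trial of approximately 80 healthy pregnant women". Section 5.2.1 allocates 1:1.

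The visit schedule in Section 5.1 fixes which sera exist:

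- Visit 1, both arms: "Obtain 15mL blood sample prior to vaccination for serologic analysis (Section 6".
- Visit 4, both arms, with the order set for one of them: "Study participants in sequential group to have blood sample obtained prior to vaccination".
- Visit 7: "Obtain 15mL blood sample for serologic analysis for sequential group only (Section 6".
- Visit 8 (delivery), both arms: maternal blood and cord blood.

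Section 2.1.1 makes influenza antibody a primary outcome in maternal blood before and after vaccination and in "Maternal and infant cord blood obtained at delivery". The Protocol Summary adds that cord serum is tested for the same antibodies as maternal serum.

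**The concern.** The assay section for a primary outcome gives a number of women 20 below the planned 80, and no section explains it. Read literally, the parenthetical could mean that a quarter of the women are left out of the influenza comparison. The total does not fit its description either. Both arms receive influenza vaccine at Visit 1 and are bled at Visits 1 and 4, so pre- and post-vaccination sera from 60 women number 120, half of 240. A reader who tries to recover which sera are meant finds more than one answer. If the description excluded delivery and cord sera, part of a primary outcome would have no assay behind it. If the laboratory planned its work on 240, the number of sera arriving could be larger.

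**Working it through.** **Inputs.** Stated figure: 60 women, 240 samples (Section 6.3). Planned women: 80 (Protocol Summary, Section 3.1). Allocation 1:1 (Section 5.2.1), so 30 per arm at 60 women and 40 per arm at 80. Sera per woman (Section 5.1): Visit 1, Visit 4, maternal delivery and cord in both arms, plus Visit 7 in the sequential arm only. Complete collection is assumed.

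**The plan's figure.** 240 / 60 = 4 sera per woman; 240 / 80 = 3 sera per woman.

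**Direct count.** Samples = sum over arms of (women per arm × sera per woman).

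| Sera counted | 60 women | 80 women |
|---|---|---|
| Visits 1 and 4 | 60 × 2 = 120 | 80 × 2 = 160 |
| Visits 1 and 4, Visit 7 (sequential) | 30 × 2 + 30 × 3 = 150 | 40 × 2 + 40 × 3 = 200 |
| Visits 1 and 4, maternal delivery | 60 × 3 = 180 | 80 × 3 = **240** |
| All maternal draws | 30 × 3 + 30 × 4 = 210 | 40 × 3 + 40 × 4 = 280 |
| Visits 1 and 4, maternal delivery, cord | 60 × 4 = **240** | 80 × 4 = 320 |
| All maternal draws and cord | 30 × 4 + 30 × 5 = 270 | 40 × 4 + 40 × 5 = 360 |

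At 60 women no maternal-only count reaches 240. It appears if cord serum is added and Visit 7 left out, or if the 120 sera from Visits 1 and 4 are counted twice because the assay is run in duplicate (120 × 2). At 80 women, 240 is exactly three maternal sera each. That matches the time points in the Protocol Summary and the limit of three maternal samplings in Section 8.3, though it omits the sequential arm's Visit 7 draw. If delivery serum counts as post-vaccination, it also fits the maternal pre/post description, and only the 60 is out of line. The documents do not settle which of the 60, the 240 or the description is the slip.

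**Possible source of the 60.** Table 6 sets a recruitment benchmark of 30 to 50 women per four-month period. Read per season, two seasons give 30 × 2 = 60 to 50 × 2 = 100, so 60 is the low end. Section 6.3 does not say so.

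**What depends on the figure.** Section 7 states that the pilot was not sized for group comparisons. Section 7.1.1 defines the ITT population as everyone randomized. Section 7.1.3.3 compares seroprotection, seroconversion and geometric mean titers by arm, with no reduced set. The biospecimen benchmarks in Table 6 are percentages collected, and Table 7 concerns pertussis testing at the CDC. None of these takes 60 or 240 as an input.

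**What the analyst needs.** Both arms receive influenza vaccine at Visit 1, so the pre/post contrast is Visit 1 against Visit 4 in each. The delivery contrast uses maternal and cord serum, as Section 2.1.1 requires. Visit 7 follows Tdap in one arm only and has no counterpart in the other.

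**The case for a change.** The strongest case for a change is that this is an unambiguous contradiction about a primary-outcome assay and one sentence would cure it. Sixty is 25% below 80 ((80 − 60) / 80), which the word approximately cannot absorb. Section 6.3 names both seasons, so 60 is not a one-season count. The only laboratory subset defined by number is the 20 infants for dried blood spots. Serum is shared between pertussis testing at the CDC and the lead site's influenza, tetanus and diphtheria assays (Section 5.5.1), so the number of HI samples could matter for aliquots. At four sera per woman the work is 80 sera more than stated, and 120 more with Visit 7. With four strains that is 80 × 4 = 320 to 120 × 4 = 480 further titrations, each in duplicate.

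The contradiction stands. The harm does not. Collection follows the visit schedule, aliquots are handled under standard procedures, and the serum left after the CDC share goes to the lead site, with shipping details in the manual of operations. No section uses the parenthetical total for any of this. Nor do the documents dictate a replacement: 240, 320 and 360 can each be argued at 80 women, and a literal reading of testing every sample gives 360. Writing in a single figure would be a guess.

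**Conclusion.** This is a clerical slip in a workload count, and no change to the plan follows. The parenthetical disagrees with planned enrollment by 20 women, and depending on which sera are counted its total is right or is low by 80 or 120 at 80 women. These sizes assume 40 women per arm and complete collection. The sentence that follows sets the testing scope to every sample, Section 2.1.1 commits to influenza antibody in delivery and cord blood, and the analysis population is everyone randomized. A laboratory or analyst following those sections would test and analyze the intended women and sera whatever the parenthetical says. No estimate, confidence interval or feasibility benchmark moves. The conclusion rests on reading the sentence about all samples, together with the outcome measures, as governing over a parenthetical count. No section of the protocol points the other way.
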